12.3.3 Methods for Evaluation of Measurable Disease

All measurements should be taken and recorded in metric notation using a ruler or calipers.

The same method of assessment and the same technique should be used to characterize each identified and reported lesion at baseline and during follow-up. Imaging-based evaluation is preferred to evaluation by clinical examination unless the lesion(s) being followed cannot be imaged but are assessable by clinical exam.

12.3.3.1 Clinical lesions: Clinical lesions will only be considered measurable when they are superficial (e.g., skin nodules and palpable lymph nodes) and ≥ 10 mm diameter as assessed using calipers (e.g., skin nodules). In the case of skin lesions, documentation by color photography, including

- a ruler to estimate the size of the lesion, is recommended.
- 12.3.3.2 Chest x-ray: Lesions on chest x-ray are acceptable as measurable lesions when they are clearly defined and surrounded by aerated lung. However, CT is preferable.
- 12.3.3.3 Conventional CT and MRI: This guideline has defined measurability of lesions on CT scan based on the assumption that CT slice thickness is 5 mm or less. If CT scans have slice thickness greater than 5 mm, the minimum size for a measurable lesion should be twice the slice thickness. MRI is also acceptable in certain situations (e.g. for body scans). Ideally, the same type of scanner should be used and the image acquisition protocol should be followed as closely as possible to prior scans.
- 12.3.3.4 PET-CT: At present, the low dose or attenuation correction CT portion of a combined PET-CT is not always of optimal diagnostic CT quality for use with RECIST measurements. However, if the site can document that the CT performed as part of a PET-CT is of identical diagnostic quality to a diagnostic CT (with IV and oral contrast), then the CT portion of the PET-CT can be used for RECIST measurements and can be used interchangeably with conventional CT in accurately measuring cancer lesions over time. Note, however, that the PET portion of the CT introduces additional data which may bias an investigator if it is not routinely or serially performed.
- 12.3.3.5 Tumor markers: Tumor markers alone cannot be used to assess response. If markers are initially above the upper normal limit, they must normalize for a patient to be considered in complete clinical response.
- 12.3.3.6 Cytology, Histology: These techniques can be used to differentiate between partial responses (PR) and complete responses (CR) in rare cases (e.g., residual lesions in tumor types, such as germ cell tumors, where known residual benign tumors can remain).
 - Cytology should be obtained if an effusion appears or worsens during treatment when the measurable tumor has met criteria for response or stable disease.
- 12.3.3.7 FDG-PET: While FDG-PET response assessments need additional study, it is sometimes reasonable to incorporate the use of FDG-PET scanning to complement CT scanning in assessment of progression (particularly possible 'new' disease). New lesions on the basis of FDG-PET imaging can be identified according to the following algorithm:
 - a. Negative FDG-PET at baseline, with a positive FDG-PET at followup is a sign of PD based on a new lesion.
 - b. No FDG-PET at baseline and a positive FDG-PET at follow-up: If the positive FDG-PET at follow-up corresponds to a new site of disease confirmed by CT, this is PD. If the positive FDG-PET at follow-up is not confirmed as a new site of disease on CT, additional

follow-up CT scans are needed to determine if there is truly progression occurring at that site (if so, the date of PD will be the date of the initial abnormal FDG-PET scan). If the positive FDG-PET at follow-up corresponds to a pre-existing site of disease on CT that is not progressing on the basis of the anatomic images, this is not PD.

Note: A 'positive' FDG-PET scan lesion means one that is FDG avid with an uptake greater than twice that of the surrounding tissue on the attenuation corrected image.

For patients with a positive PET scan at diagnosis, PET can be used to follow response in addition to a CT scan using the International Pediatric non-Hodgkin Lymphoma Response Criteria. 55

12.4 Response Criteria for Patients with Solid Tumor and Measurable Disease

12.4.1 **Evaluation of Target Lesions**

Complete Response (CR): Disappearance of all target and non-target

lesions. Any pathological lymph nodes (whether target or non-target) must have reduction in short axis to <10 mm. If immunocytology is available, no disease must be detected by that methodology. Normalization of tumor markers if elevated at study enrollment (for patients with

neuroblastoma).

Partial Response (PR): At least a 30% decrease in the sum of the

diameters of target lesions, taking as reference the

baseline sum diameters

Progressive Disease (PD): At least a 20% increase in the sum of the

diameters of target lesions, taking as reference the smallest sum on study (this includes the baseline sum if that is the smallest on study). In addition to the relative increase of 20%, the sum must also demonstrate an absolute increase of at least 5 mm. (Note: the appearance of one or more new lesions is also considered progressions). Note: in presence of SD or PR in target disease but unequivocal progression in non-target or nonmeasurable disease, the patient has PD if there is an overall level of substantial worsening in nontarget disease such that the overall tumor burden has increased sufficiently to merit

discontinuation of therapy

Stable Disease (SD): Neither sufficient shrinkage to qualify for PR nor

sufficient increase to qualify for PD, taking as

reference the smallest sum diameters while on study

12.4.2 **Evaluation of Non-Target Lesions**

Complete Response (CR): Disappearance of all non-target lesions and

normalization of tumor marker level. All lymph nodes must be non-pathological in size (<10 mm

short axis)

Note: If tumor markers are initially above the upper normal limit, they must normalize for a patient to be considered in complete clinical

response.

Non-CR/Non-PD: Persistence of one or more non-target lesion(s)

and/or maintenance of tumor marker level above

the normal limits

Progressive Disease (PD): Appearance of one or more new lesions and/or

unequivocal progression of existing non-target lesions. Unequivocal progression should not normally trump target lesion status. It must be representative of overall disease status change,

not a single lesion increase.

12.4.3 Overall Response Assessment

Table 1: For Patients with Measurable Disease (i.e., Target Disease)

Target	Non-Target	New	Overall	Best Overall Response
Lesions	Lesions	Lesions	Response	when Confirmation is
				Required*
CR	CR	No	CR	≥ 28 days Confirmation
CR	Non-	No	PR	
	CR/Non-PD			≥ 28 days Confirmation
CR	Not evaluated	No	PR	
PR	Non-	No	PR	
	CR/Non-			
	PD/not			
	evaluated			
SD	Non-	No	SD	documented at least once ≥
	CR/Non-			28 days from baseline
	PD/not			-
	evaluated			
PD	Any	Yes or No	PD	
Any	PD**	Yes or No	PD	no prior SD, PR or CR
Any	Any	Yes	PD	

^{*} See RECIST 1.1 manuscript for further details on what is evidence of a new lesion.

Note: Patients with a global deterioration of health status requiring discontinuation of treatment without objective evidence of disease progression at that time should be

^{**} In exceptional circumstances, unequivocal progression in non-target lesions may be accepted as disease progression.

reported as "symptomatic deterioration." Every effort should be made to document the objective progression even after discontinuation of treatment.

Table 2: For Patients with Non-Measurable Disease (i.e., Non-Target Disease)

Non-Target Lesions	New Lesions	Overall Response
CR	No	CR
Non-CR/non-PD	No	Non-CR/non-PD*
Not all evaluated	No	not evaluated
Unequivocal PD	Yes or No	PD
Any	Yes	PD

^{* &#}x27;Non-CR/non-PD' is preferred over 'stable disease' for non-target disease since SD is increasingly used as an endpoint for assessment of efficacy in some trials so to assign this category when no lesions can be measured is not advised

Table 3: Overall Response for Patients with Neuroblastoma and Measurable Disease

CT/MRI	MIBG	Bone Marrow	Overall
PD	Any	Any	PD
Any	PD	Any	PD
Any	Any	Any	PD
Any	Any	PD	PD
SD	CR/PR/SD	Non-PD	SD
PR	CR/PR	Non-PD	PR
CR/PR	PR	Non-PD	PR
CR	CR	Non-PD	PR
CR	CR	CR	CR

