11.4 Methods of Analysis

Response criteria are described in Section 12. A responder is defined as a patient who achieves a best response of PR or CR on the study. Response rates will be calculated as the percent of evaluable patients who are responders, and confidence intervals will be constructed using the Wilson score interval method.⁵⁴ Decision making for A'Hern design cohorts will follow rules described above.

Toxicity tables will be constructed to summarize the observed incidence by type of toxicity and grade. A patient will be counted only once for a given toxicity for the worst grade of that toxicity reported for that patient. Toxicity information recorded will include the type, severity, time of onset, time of resolution, and the probable association with the study regimen.

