12.3 Response Criteria for Patients with Solid Tumors

See the table in Section 8.0 for the schedule of tumor evaluations. In addition to the scheduled scans, a confirmatory scan should be obtained on the next consecutive cycle following initial documentation of objective response.

As outlined, patients will be assigned to one of the following categories for assessment of response: a) solid tumor (non-CNS) and measurable disease (Section 12.4); b) neuroblastoma with MIBG positive lesions (Section 12.5); c) CNS tumor (Section 12.7); and d) lymphoma/histiocytosis (Section 12.8). Note: Neuroblastoma patients who do not

have MIBG positive lesions should be assessed for response as solid tumor patients with measurable disease.

Response and progression will be evaluated in this study using the revised Response Evaluation Criteria in Solid Tumors (RECIST) guideline (version 1.1) [Eur J Ca 45:228-247, 2009]. Key points are that 5 target lesions are identified and that changes in the largest diameter (unidimensional measurement) of the tumor lesions but the shortest diameter of malignant lymph nodes are used in the RECIST v 1.1 criteria.

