12.5 Response Criteria for Neuroblastoma Patients

This study will use the revised International Neuroblastoma Response Criteria for disease assessment.⁵⁶ The updated response criteria incorporate current approaches to imaging of neuroblastoma, including functional imaging. Furthermore, a standardized approach to assessment of bone marrow involvement is included. The current INRC do **not** include methods of disease assessment that are less sensitive and/or specific for neuroblastoma (⁹⁹Tc bone scan and catecholamine levels).

Key sites and terms

Primary site: The primary site will be identified as a measurable lesion ≥ 10 mm in diameter as assessed by cross sectional imaging (CT or MRI scan). Primary site measurements must be recorded in millimeters (or decimal fractions of centimeters). The longest diameter of the primary tumor will be recorded at baseline. Serial measurements of the primary tumor will include assessment of tumor size in the same orthogonal plane at the time of each evaluation. In patients with bilateral adrenal lesions, response will be based on the sum of the longest dimensions of both adrenal lesions unless biopsy proves one to be ganglioneuroma rather than neuroblastoma/ganglioneuroblastoma. In patients with multi-focal non-adrenal disease, the largest

tumor will be considered the primary tumor. Response in additional lesions will be assessed as described below for metastatic lesions.

Tracer avidity (¹²³I-MIBG or FDG-PET) in the primary site will be recorded at baseline. The scan appropriate for serial disease assessments should be used at each disease re-evaluation timepoint (e.g. ¹²³I-MIBG avid primary lesions should be followed using ¹²³I-MIBG scans during therapy).

Malignant lymph nodes: To be considered pathologically enlarged and measurable, a metastatic lymph node must be ≥ 15 mm in short axis when assessed by CT or MRI scan (CT scan slice thickness recommended to be no greater than 5 mm). At baseline and in follow-up, only the short axis of a discreet lymph node will be measured and followed as per RECIST criteria. Patients with neuroblastoma may have conglomerate masses of non-discrete lymph nodes (i.e. multiple contiguous retroperitoneal nodes). When a short axis of a discreet node cannot be identified, a lymph node conglomerate can be measured using the longest diameter of the composite lesion. Tracer avidity of metastatic nodes will be recorded at baseline and during disease evaluations.

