Minimal disease (MD)	 Any of the following: Bone marrow with ≤ 5% tumor infiltration and remains > 0-≤ 5% tumor infiltration upon reassessment; or Bone marrow with no tumor infiltration that becomes ≤ 5% tumor infiltration upon reassessment; or Bone marrow with >20% tumor infiltration that has > 0-≤ 5% tumor infiltration upon reassessment.
Stable disease (SD)	Bone marrow with tumor infiltration that remains positive with > 5% tumor infiltration upon reassessment but does not meet CR, MD or PD criteria

¹Immunohistochemistry strongly encouraged

DETERMINATION OF OVERALL RESPONSE

RESPONSE	CRITERIA
Complete Response (CR)	All components meet criteria for CR
Partial Response (PR)	PR in at least one component and all other components are either CR, MD (Bone marrow), PR (Soft tissue or Bone) or Not involved (NI); no component with PD.
Minor Response (MR)	PR or CR in at least one component but at least one other component with SD; no component with PD.
Stable Disease (SD)	SD in one component with no better than SD or NI in any other component; no component with PD.
Progressive Disease (PD)	Any component with PD

NI = Not involved, site not involved at study entry and remains not involved; MD = Minimal Disease, for bone marrow assessment only.

Overall Best Response Assessment

Each patient will be classified according to his "best response" for the purposes of analysis of treatment effect. Best response is determined as outlined in Section 12.8 from a sequence of overall response assessments.

Primary Tumor	Soft Tissue and Bone Metastatic Disease (MIBG or FDG-PET or PET/MR)	Bone Marrow Metastatic Disease	Overall
CR	CR	CR	CR
	CR for one response component with either CR or NI for		CR
CR	CR	MD	PR
CR	PR	CR	PR
CR	PR	MD	PR
CR	PR	NI	PR
CR	NI	MD	PR
PR	CR	CR	PR
PR	CR	NI	PR
PR	CR	MD	PR
PR	PR	CR	PR
PR	PR	NI	PR
PR	PR	MD	PR
PR	NI	CR	PR
PR	NI	NI	PR
PR	NI	MD	PR
NI	CR	MD	PR
NI	PR	CR	PR
NI	PR	MD	PR
CR	CR	SD	MR
CR	PR	SD	MR
CR	SD	CR	MR
CR	SD	MD	MR
CR	SD	SD	MR
CR	SD	NI	MR
CR	NI	SD	MR
PR	CR	SD	MR
PR	PR	SD	MR
PR	SD	CR	MR
PR	SD	MD	MR
PR	SD	SD	MR
PR	SD	NI	MR
PR	NI	SD	MR
SD	CR	CR	MR
SD	CR	MD	MR
SD	CR	SD	MR
SD	CR	NI	MR
SD	PR	CR	MR
SD	PR	MD	MR
SD	PR	SD	MR
SD	PR	NI	MR
SD	SD	CR	
SD SD	SD NI	CR CR	MR MR
NI	CR	SD	MR
NI NI		SD SD	
NI NI	PR SD		MR
		CR	MR
SD	SD	MD MD	SD
NI	SD	MD MD	SD
SD	NI NI	MD MD	SD
NI	NI GD	MD	SD
SD	SD	SD	SD
SD	NI	SD	SD
NI NI	SD	SD	SD
NI	SD	NI	SD
NI	NI	SD	SD
	PD in any one component	nor at study enrollment and no PD for any component	PD Not Evalua

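### For neuroblastoma, Table 3 counts responding disease with stable marrow involvement as PR, while Section 12.5.1 counts the same findings as Minor Response, a non-response

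*Combined protocol and SAP*

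**What the plan says.** Section 12.4.3, within the solid-tumor criteria, contains "Table 3: Overall Response for Patients with Neuroblastoma and Measurable Disease". Its columns are CT/MRI, MIBG, bone marrow and overall response. One row reads "PR CR/PR Non-PD PR". The rows for CT/MRI CR or PR with MIBG PR, and for CT/MRI CR with MIBG CR, likewise give PR when the marrow is Non-PD.

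Section 12.5 opens differently: "This study will use the revised International Neuroblastoma Response Criteria for disease assessment". Section 12.5.1 then defines overall PR as "PR in at least one component and all other components are either CR, MD (Bone marrow), PR (Soft tissue or Bone) or Not involved", and Minor Response (MR) as "PR or CR in at least one component but at least one other component with SD; no component with PD". Stable marrow disease is "Bone marrow with tumor infiltration that remains positive with > 5% tumor infiltration upon reassessment but does not meet CR, MD or PD criteria".

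Section 12.3 sends neuroblastoma with MIBG-positive lesions to Section 12.5. Its note concerns neuroblastoma patients who do not "have MIBG positive lesions should be assessed for response as solid tumor patients with measurable disease".

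Section 11.4 fixes the endpoint: "A responder is defined as a patient who achieves a best response of PR or CR on the study". MR does not appear in the best-response rules of Section 12.8. Section 11.3.1 declares success at 3 or more responses in 20.

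**The concern.** Marrow that is stable by the 12.5.1 definition has, by that same definition, not progressed. It therefore satisfies the Non-PD entry in Table 3. A patient whose imaging responds on both CT/MRI and MIBG, but whose marrow stays more than 5% infiltrated, is PR by one table and MR by the other.

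The difference reaches the primary endpoint, because PR counts toward the 3-of-20 rule and MR does not. Patients with known marrow metastases may enroll if they meet the blood counts (Section 4.1.7.1), and a footnote to the Section 8.1 table calls for marrow examination when CR or PR is seen in target disease. The protocol therefore generates the marrow result on which the two tables disagree.

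A related tension concerns MIBG-negative neuroblastoma. The 12.3 note sends these patients to the solid-tumor criteria, yet 12.5 gives FDG-PET criteria for MIBG non-avid tumors and Section 8.1 requires PET for patients with no current or past MIBG-avid tumor.

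**Working it through.** **1. The plan's own figure.** Inputs from Section 11.3.1: N = 20, success at 3 or more responses, null rate 5%, target rate 25%, stated alpha 10% and power 90%. With X binomial(20, p):

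- P(X ≥ 3 | 0.05) = 1 − [0.95^20 + 20(0.05)(0.95^19) + 190(0.05²)(0.95^18)] = 0.0755
- P(X ≥ 3 | 0.25) = 1 − [0.75^20 + 20(0.25)(0.75^19) + 190(0.25²)(0.75^18)] = 0.9087

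The design reproduces. An exact alpha of 7.55% against a limit of 10% is ordinary discreteness, not an error.

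**2. The two rules side by side, marrow stable.**

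| CT/MRI | MIBG | Marrow | Table 3 | 12.5.1 |
|---|---|---|---|---|
| CR | CR | SD | PR | MR |
| CR | PR | SD | PR | MR |
| PR | CR | SD | PR | MR |
| PR | PR | SD | PR | MR |

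This lines up CT/MRI with the primary-tumor column of the 12.5.1 grid, and MIBG with its metastatic column. The result does not depend on that alignment. Under the 12.5.1 text, any component with SD rules out PR and CR, whichever column the imaging falls in.

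**3. All combinations without progression.** There are 3 (CT/MRI: CR, PR, SD) × 3 (MIBG: CR, PR, SD) × 4 (marrow: CR, minimal disease, SD, not involved) = 36. Leaving aside the Any/Any/Any row of Table 3, 22 of the 36 get a different label or have no row in Table 3:

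- 4 change responder status (the table above).
- 9 are SD in Table 3 and MR in 12.5.1: non-response in both.
- 8 (CT/MRI CR or PR with MIBG SD) have no row in Table 3 and are MR in 12.5.1.
- 1 (CR/CR, marrow not involved) is PR in Table 3 and CR in 12.5.1: response in both.

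Check: 4 + 9 + 8 + 1 = 22.

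**4. When one such patient decides the trial.** Suppose exactly one of the 20 is discordant. The label is decisive when exactly 2 of the other 19 respond, with probability 171 p²(1 − p)^17:

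| True response rate p | Calculation | Probability |
|---|---|---|
| 5% | 171 × 0.0025 × 0.4181 | 17.9% |
| 10% | 171 × 0.01 × 0.1668 | 28.5% |
| 15% | 171 × 0.0225 × 0.0631 | 24.3% |
| 25% | 171 × 0.0625 × 0.00752 | 8.0% |

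Put another way, the chance of meeting the rule at p = 5% is 24.5% if that patient counts as PR (2 or more of 19 needed) and 6.7% if counted as MR (3 or more of 19). At p = 25% it is 96.9% against 88.9%.

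**5. How often it may arise.** The protocol gives no expected number. Section 2.1.1 reports, for a neuroblastoma data set of 1089, 3 HRAS copy-number cases and no single-nucleotide variants. It also reports 1 neuroblastoma among 109 HRAS-mutated cases in a 10,000-case series. The HRAS mutations it reports from Pediatric MATCH screening are 6, in rhabdomyosarcoma, among 769 patients screened. The variants listed in Appendix VIII are all single- or multi-nucleotide changes. A discordant patient must also have marrow disease that stays above 5%, and respond on both imaging components.

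**The case against.** The strongest reply is that the protocol already says which rule applies. Section 12.3 routes MIBG-positive neuroblastoma to 12.5, and 12.5 adopts the revised INRC. Table 3 sits in the solid-tumor section and looks like a leftover. Most of this stands: 12.5.1 is very probably the intended rule, and a reader who inferred that the plan gives no guidance would be wrong. What remains is that nothing withdraws Table 3. Its title names neuroblastoma, and its SD, PR and CR rows all need an MIBG result, so they describe the very patients sent to 12.5.

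The second reply, rarity, also stands. A reader might take the 8.0% to 28.5% as the chance that the ambiguity changes the trial's conclusion. They are conditional on one discordant patient being enrolled; the unconditional chance is much smaller and cannot be computed from the documents. That neuroblastoma is among the 20 entries in Appendix VII adds little.

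Three other inferences are not supported:

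- The Any/Any/Any row of Table 3, as it reads here, would make every patient PD. It may have lost a cell in text extraction, so nothing rests on it.
- The SD-versus-MR differences look like further conflicts on the endpoint, but both labels are non-response.
- It is tempting to say that the label will be chosen after results are seen. Responses require central review (Section 11.5), so that is conjecture, although no table is named for the review to use.

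**Conclusion.** The conflict is real and narrow. For neuroblastoma with measurable disease, four combinations of imaging response with stable marrow are PR under Table 3 and MR under 12.5.1, and only the first counts toward the primary endpoint. This rests on reading Non-PD literally, which the marrow SD definition supports. Section 12.5.1 appears meant to govern, and affected patients are probably few. If exactly one is enrolled, and the other 19 respond independently at a common rate, the label decides the result 8.0% to 28.5% of the time over true rates of 5% to 25%. The sample size and the decision rule are unaffected. It is worth correcting because the threshold is only three responses and the correction is cheap.

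A reader might go further and conclude that MIBG-negative patients should be moved to the 12.5 criteria. The documents do not support that. The 12.3 note is an explicit choice, and the tension with 12.5 and 8.1 calls for reconciliation only.

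**What to change.** Delete Table 3 from Section 12.4.3, or align its marrow column with 12.5.1. State in Sections 12.3 and 12.5 that the 12.5.1 table alone determines overall response for neuroblastoma patients routed to 12.5, for institutional and central review alike. State in Section 11.4 or 12.8 that MR is non-response.

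Separately, reconcile the 12.3 note on MIBG-negative patients with the FDG-PET criteria in 12.5 and the PET requirement in 8.1. This point does not say which should apply. The choice has consequences beyond wording: Section 12.5 asks for bilateral marrow aspirates and trephine biopsies at disease assessment timepoints, whereas 8.1 limits marrow sampling to specified circumstances.

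The Table 3 change costs a wording amendment, with no new imaging and no change to the design. Its downside is a slightly stricter PR for patients with stable marrow disease than Table 3 would give. It should be made before responses are adjudicated.
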